6.8 Development of the models

6.8.1 Model development overview

We will use the following steps:

- 1. Development of prognostic models for each outcome within the derivation data.
- 2. Evaluation of predictive performance in the validation data.

Separate models will be developed and evaluated for males and females.

6.8.2 Development of the models using the derivation data

For all analyses, the time origin is entry to the study cohort and the risk period of interest is from the time origin up to the first date of diagnosis of oesophageal cancer. We will develop and evaluate the risk prediction equations using established methods^{19 32-35} We will use second degree fractional polynomials (i.e. with up to two powers)³¹ to model non-linear relationships for continuous variables (age, body mass index and Townsend score). Models will include interactions between age and predictor variables focussing on predictor variables which apply across the age range where numbers allow.

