6.2.3 Patient exclusions

Exclusions will broadly match those for WP2 which aims to implement the risk algorithm for recalling patients for the Cytosponge and hence the following will be excluded

- Patients with a new onset of alarm symptoms (including haematemesis, unexplained weight loss, dysphagia) in the last 3 months before study entry since these are likely to require urgent referral on the 2-Week Wait pathway for endoscopy.
- Recorded diagnosis of a current or previous oro-pharynx, oesophageal or gastrooesophageal tumour
- Received prior surgical intervention to the oesophagus
- Recorded oesophageal varices, cirrhosis of the liver

Patients with recorded Barrett's oesophagus will be included and the presence of Barrett's oesophagus will be evaluated as a risk factor.

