6.3 Study period

Patients will enter the cohort on the latest of the study start date or the date on which they become 25 or 12 months after registering with their GP practice. Patients will be followed up until they develop oesophageal cancer, die, leave the practice or the study end date or a maximum follow up period of 15 years.

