6.5 Secondary outcome

Our secondary outcome is the diagnosis of Barrett's Oesophagus.

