6.6.4 Co-morbidities and investigations

- 8. gastric cancer
- 9. Barrett's oesophagus*
- 10. Peptic ulcer disease*
- 11. Gastro-oesophageal reflux disease (including heart burn)
- 12. Type 1 and type 2 diabetes*
- 13. previous blood cancer*
- 14. previous breast cancer*
- 15. previous oral cancer*
- 16. previous pancreatic cancer*
- 17. Current H.Pylori infection (which may lower OAC risk)
- 18. pernicious anaemia
- 19. hiatus hernia
- 20. anaemia (including Haemoglobin values)
- 21. Full blood count
- 22. CT scan abdomen within the previous 5 years
- 23. CT scan pelvis within the previous 5 years
- 24. Barium meal/swallow within the previous 5 years
- 25. Endoscopy within the previous 5 years

All predictor variables will be based on the latest coded information recorded in the GP record prior to entry to the cohort.

6.7 **Descriptive analysis**

We will produce the following descriptive analyses for comparison with the literature and national statistics from the CRUK website.

- crude incidence of oesophageal cancer by age, sex, ethnicity, deprivation and calendar time.
- age standardised incidence of oesophageal cancer overall and by type.
- characteristics of cases diagnosed with oesophageal cancer age at diagnosis, stage, grade, histology, treatment (surgery, radiotherapy, chemotherapy, other).

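### Barrett's diagnosis is the secondary outcome, but the rules for cohort, predictors, risk period and imputation fit only the oesophageal cancer outcomes

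*Protocol*

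**What the plan says.** The secondary outcome is defined in one sentence of Protocol 6.5: "Our secondary outcome is the diagnosis of Barrett's Oesophagus". The first modelling step in 6.8.1 is "Development of prognostic models for each outcome within the derivation data".

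The rules that those models would follow are these:

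- **Cohort (6.2.3):** "Patients with recorded Barrett's oesophagus will be included and the presence of Barrett's oesophagus will be evaluated as a risk factor". There is one exclusion list for the whole study.
- **Predictors (6.6.4):** the list contains "9. Barrett's oesophagus". On timing, "All predictor variables will be based on the latest coded information recorded in the GP record prior to entry to the cohort". Section 6.8.4 then starts from models that contain every predictor.
- **Risk period (6.8.2):** a sentence that is stated to cover every analysis says that "the risk period of interest is from the time origin up to the first date of diagnosis of oesophageal cancer".
- **Follow-up (6.3):** "Patients will be followed up until they develop oesophageal cancer, die, leave the practice or the study end date or a maximum follow up period", which the section sets at 15 years. A Barrett's diagnosis is not among these end points.
- **Imputation (6.8.3):** the outcome indicators are specified as oesophageal cancer alone.

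The only rule that removes prevalent cases outcome by outcome is the footnote to the Table 2 shell, and it speaks of cancers only.

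**The concern.** Someone who already has recorded Barrett's cannot have a first Barrett's diagnosis. A model for that outcome needs a cohort free of the condition at entry and a clock that stops when it is first recorded. The protocol provides neither. It states rules of general scope that give the wrong risk set, an inadmissible predictor and the wrong terminating diagnosis for one of its two named outcomes.

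At stake is the interpretation of the Barrett's results. As written, the incidence, hazard ratios, discrimination and calibration would not be those of newly diagnosed Barrett's. Two analysts working from the same text could also resolve the conflict differently and report different models.

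**Working it through.** The protocol gives no event rate, sample size or other figure specific to the Barrett's outcome, so there is none to reproduce. The check compares the stated rules with what each outcome needs and then sizes the affected group.

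**Step 1: rules against outcomes**

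- *Inclusion of people with recorded Barrett's (6.2.3).* Coherent for cancer, because they are at risk of it. Not coherent for a first Barrett's diagnosis.
- *Barrett's as predictor 9, taken from records before entry (6.6.4).* For cancer this is a legitimate prevalent risk factor. For Barrett's the predictor is the outcome already present.
- *Risk period ending at oesophageal cancer (6.8.2), with 6.3 not listing Barrett's.* Correct for cancer. For Barrett's the event that should end the period is missing.
- *Imputation outcome terms (6.8.3).* Cancer is represented; Barrett's is not.

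All four rules fit the cancer outcomes, and none fits Barrett's. No section sets a different rule for it.

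**Step 2: what happens to a prevalent case in a Barrett's model**

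There are three possibilities, and the protocol does not choose among them:

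1. A later Barrett's code counts as the event. The coefficient for baseline Barrett's then measures re-coding, and the retention rule in 6.8.4 (hazard ratio outside 0.90 to 1.10, significant at 0.01) could keep it.
2. The person stays in as a non-event. They add time at risk with no possibility of a first diagnosis, and the coefficient reflects that impossibility.
3. The person is dropped. The risk set is then right and the predictor is constant, but 6.2.3 has not been followed.

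Only the third is valid, and it departs from the text.

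**Step 3: size of the affected group**

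Inputs, all from Protocol 4.1:

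- share of people with reflux-predominant symptoms who may have Barrett's: 3% to 6%;
- share of patients with Barrett's who are diagnosed: about 20%;
- share of the population with heartburn symptoms: 5% to 20%.

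Recorded Barrett's among people with reflux symptoms:

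- low: 0.03 × 0.20 = 0.006, or 6,000 per million;
- high: 0.06 × 0.20 = 0.012, or 12,000 per million.

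The cohort is the registered population aged 25 to 90 (6.2.2), not people with reflux, so these shares are multiplied by the heartburn prevalence:

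- low: 0.006 × 0.05 = 0.0003, or 300 per million cohort members;
- high: 0.012 × 0.20 = 0.0024, or 2,400 per million cohort members.

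This counts only recorded cases with reflux symptoms. It assumes that heartburn and reflux-predominant symptoms can be equated and that the figures in 4.1 hold for this cohort. The inconsistency in Step 1 does not depend on the estimate.

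**The case against.** The strongest reply is that no Barrett's model is ever described. The plural in 6.8.1 could refer to the cancer outcomes alone, since 6.4 already divides the primary outcome into all types, adenocarcinoma and squamous cell cancer. The objectives, descriptive analyses, risk categories and table shells all concern cancer. On this view the inclusion rule and predictor 9 were never meant for Barrett's, and the details of a secondary outcome may sit in an analysis plan that is not shown. The authors also know how to drop prevalent cases, as the Table 2 footnote shows. If the earliest-recorded-date rule of 6.4 were carried over, a prevalent case would have an event before entry and no time at risk.

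Part of this stands. The Barrett's model is inferred from 6.5 and 6.8.1 together, and it is not certain that prevalent cases would be mishandled in practice. It does not remove the point. The text of 6.8.2 covers all analyses, so an analysis plan that treated Barrett's correctly would have to contradict 6.2.3 and 6.8.2. The footnote covers cancers only, and the date rule in 6.4 is stated only for the primary outcome. If no Barrett's model is intended, 6.8.1 should say so.

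A reader might also infer more than the documents support:

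- *That the cancer models are compromised.* They are not; every rule at issue is sound for them.
- *That use of the tool is undermined because Cytosponge looks for Barrett's.* The five uses listed in section 5 rest on the oesophageal cancer algorithm, and none mentions a Barrett's model.
- *That 6,000 to 12,000 prevalent cases per million sit in the risk set.* That range applies to people with reflux symptoms, not to the general cohort.
- *That follow-up ends at nothing but cancer.* Section 6.3 also ends it at death, leaving the practice, study end and 15 years. What is missing is Barrett's diagnosis.

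**Conclusion.** The concern holds for the secondary outcome. As written, a Barrett's model would have the wrong risk set, would contain its own outcome as a predictor, would lack the right terminating diagnosis, and would be imputed without its outcome. The people wrongly in the risk set number roughly 300 to 2,400 per million cohort members, under the assumptions stated with the calculation. The effect on a hazard ratio, C statistic or calibration cannot be derived from the documents and is not claimed.

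The conclusion rests on reading 6.8.1 as including the outcome named in 6.5, which is its plain sense. Severity is moderate: the primary analysis is untouched, but the secondary one cannot be run validly without departing from the protocol.

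**What to change.** Limit the risk-period sentence in 6.8.2 to the oesophageal cancer outcomes, and keep the present inclusion rule and predictor 9 for those. For analyses of Barrett's diagnosis, add that:

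- patients with Barrett's recorded on or before cohort entry are excluded (6.2.3);
- predictor 9 is removed from the candidate list (6.6.4);
- the risk period ends at the first recorded Barrett's diagnosis, or at oesophageal cancer, death, leaving the practice, study end or 15 years if earlier (6.3 and 6.8.2);
- the imputation model for these analyses includes the Barrett's outcome indicator and its cumulative hazard (6.8.3).

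If no Barrett's model is planned, say so in 6.8.1 and state what will be reported for the outcome in 6.5. Modelling cancer and death as competing events is optional and is not needed to cure this defect.

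The cost is a few sentences across those sections, plus a separate imputation run for the Barrett's cohort. No new data are needed.

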6.8.3 Handling of missing data

For all predictor variables, we will use the most recently available value at the time origin. For indicators of co-morbidities and medication use, the absence of information being recorded is assumed to mean absence of the factor in question. There may be missing data in some variables due to never being recorded: ethnicity, Townsend score, body mass index, smoking status and alcohol intake. We will use multiple imputation with chained equations to replace missing values for these variables ³⁶⁻³⁹.

Prior to the imputation, a complete-case analysis will be fitted using a model containing only the continuous covariates within the derivation data to derive the fractional polynomial order and corresponding powers. Then a multiple imputation model using chained equations will be fitted in the derivation data and will include all predictor variables along with age interaction terms, the Nelson–Aalen estimators of the baseline cumulative hazard, and the outcome indicators (namely, oesophageal cancer). Separate imputation models will be fitted for men and women. We will carry out 5 imputations as this has a relatively high efficiency²⁹ and is a pragmatic approach accounting for the size of the datasets and capacity of the available servers and software.

Each analysis model will be fitted in each imputed data set. We will use Rubin's rules to combine the model parameter estimates across the imputed datasets⁴⁰.

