2.4 Vision

To re-design and evaluate the clinical pathway such that we systematically identify those at risk, perform a simple test to inform who needs endoscopy and in so doing rationalise the use of long-term PPI medication. Due to the cost-effectiveness of Cytosponge-TFF3 compared with endoscopy these changes will likely result in an economic benefit to the NHS, a social benefit for early detection of a lethal cancer and a reduction in over-use of PPI medication.

3 Summary Work Package 1

- **Objective** To derive and evaluate a risk prediction tool to predict oesophageal cancer (all types and according to squamous or adenocarcinoma subtype) which can be applied in primary care to identify high risk patients suitable for assessment with the Cytosponge in primary care.
- Design Prospective population based open cohort study using routinely collected data from 1500 GP practices in England in the QResearch database (derived from EMIS electronic medical records) between 01.01.2000 and 31.12.2020 (or latest data available). We will use the QResearch database to develop the risk equations. Models will be developed on a derivation dataset from a subset of approximately 1100 practices and validated in the remaining 400 practices. The model will be externally evaluated in other relevant datasets as they become available.
- Subjects We will study adults aged 40 years and over who are free of oesophageal cancer at study entry. Patients with a new onset of alarm symptoms (e.g. dysphagia, weight loss etc) in the preceding 3 months will also be excluded.
- Methods Cox time-to-event models will be used in the derivation data to derive separate risk equations in males and females for estimating risk of oesophageal cancer. Predictors considered will include age, ethnicity, deprivation, smoking status, alcohol intake, body mass index, pre-existing medical co-morbidities, and concurrent medication. Measures of performance (prediction errors, calibration and discrimination) will be determined in the validation data for men and women separately and by ten-year age group.
- **Outcome** Our primary outcome is oesophageal cancer defined as recorded on GP record or linked hospital, cancer registry or death certificate.

4 Background

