6.4 Primary Outcome

Our primary outcome of interest is the diagnosis of oesophageal cancer during follow up (all

types and subdivided into adenocarcinoma or squamous cell cancer). We will ascertain the diagnoses on the basis of a diagnosis recorded in any of the four linked data sources (1) patients GP record (2) on their linked mortality record (3) hospital record or (4) cancer registry record. We will use the earliest recorded date of oesophageal cancer diagnosis on any of the four data sources as the index date.

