6.8.6 Validation of the models

In the validation data, we will fit an imputation model to enable imputation of missing values for ethnicity, body mass index, alcohol and smoking status. We will carry out 5 imputations. We will apply the risk equations for males and females obtained from the derivation data to the validation data and calculate measures of performance.

As in previous studies⁴², we will calculate R² values (explained variation where higher values indicate a greater proportion of variation in survival time explained by the model ⁴³), D statistics⁴⁴ (a measure of discrimination which quantifies the separation in survival between patients with different levels of predicted risk where higher values indicate better discrimination), Brier scores, and Harrell's C statistics at 1, 2, 5 and 10 years and combine these across datasets using Rubin's rules. Harrell's C statistic⁴⁵ is a measure of discrimination (separation) which quantifies the extent to which those with earlier events have higher risk scores. Higher values of Harrell's C indicate better performance of the model for predicting

the relevant outcome. A value of 1 indicates that the model has perfect discrimination. A value of 0.5 indicates that the model discrimination is no better than chance.

We will calculate 95% confidence intervals for the performance statistics to allow comparisons with alternative models for the same outcome and across different subgroups.⁴⁶

We will assess calibration of the risk scores by comparing the mean predicted risks with the observed risks by tenth of predicted risk. The observed risks will be obtained using Kaplan-Meier estimates evaluated at 10 years, obtained for men and women.

We will also evaluate these performance measures in 6 pre-specified age groups (25-49; 50-59; 60-69; 70-79; 80+), and in people on long term PPIs.

We will also compare the risk prediction model with a simple algorithm based only on criteria such as age and number of electronic prescriptions of PPI/H2 blockers and consider the use of decision curve analysies.

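### The derivation imputation conditions on overall oesophageal cancer only, which pulls the adenocarcinoma and squamous coefficients together where they differ; Townsend score is also missing from the validation imputation list

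*Protocol*

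**What the plan says.** **Outcomes to be modelled.** The objective in section 3 (Summary Work Package 1) is a tool to "predict oesophageal cancer (all types and according to squamous or adenocarcinoma subtype". Section 6.4 defines the primary outcome as all "types and subdivided into adenocarcinoma or squamous cell cancer". Section 6.5 adds: "Our secondary outcome is the diagnosis of Barrett's Oesophagus". Step 1 of section 6.8.1 is "Development of prognostic models for each outcome within the derivation data".

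**Derivation imputation.** Section 6.8.3 names the incompletely recorded variables as "ethnicity, Townsend score, body mass index, smoking status and alcohol intake". The chained-equation model is to hold all predictors, age interactions and "the Nelson–Aalen estimators of the baseline cumulative hazard", followed by "and the outcome indicators (namely, oesophageal cancer". Men and women are imputed separately. No split by outcome is mentioned, and each analysis model is to be fitted in each imputed data set.

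**Validation imputation.** Section 6.8.6 provides for "imputation of missing values for ethnicity, body mass index, alcohol and smoking status". Townsend score is not in that list, although sections 6.6.1 and 6.8.2 make it a candidate predictor with a fractional polynomial form.

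**The concern.** An imputation model should contain the outcome of the analysis that will use the imputed values. Section 6.8.3 accepts this by including an outcome indicator and cumulative-hazard terms, but as written it does so only for oesophageal cancer as a whole. Take an adenocarcinoma case and a squamous case with the same other covariates and the same follow-up. If BMI is missing in both, both draw it from the same distribution, one that reflects a blend of the two histologies. A subtype model fitted to those values recovers part of its own effect and part of the blend.

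At stake are the subtype equations, which belong to the primary outcome. The distortion is a bias, so the large sample described in section 6.8.9 does not reduce it. The retention rule in section 6.8.4 also works on these coefficients, so variable selection could be affected, although no such effect has been demonstrated.

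The Townsend point is separate and smaller. Section 6.8.3 allows for missing Townsend scores, but section 6.8.6 does not say how a validation patient without one is to be scored.

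**Working it through.** The protocol gives no missing fractions, subtype effects or other figure on this point, so there is nothing of its own to reproduce. All effect sizes and missing fractions below are assumptions.

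**Approximation.** Let *p* be the fraction missing, and *b1* and *b2* the true log hazard ratios for adenocarcinoma and squamous cancer. Assume two adenocarcinoma events for each squamous event. Observed values carry the subtype's own effect, and imputed values carry the event-weighted average:

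log HR_k (estimated) ≈ (1 − p)·b_k + p·(2·b1 + b2)/3

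The gap between the two log hazard ratios is therefore multiplied by about (1 − p), whatever the event weights.

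**Modest divergence, p = 0.30, true HRs 1.40 and 1.20.** b1 = 0.336, b2 = 0.182, average = (0.673 + 0.182)/3 = 0.285.
- Adenocarcinoma: 0.7 × 0.336 + 0.3 × 0.285 = 0.321, HR 1.38.
- Squamous: 0.7 × 0.182 + 0.3 × 0.285 = 0.213, HR 1.24.

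**Strong divergence, p = 0.30, true HRs 1.40 and 0.60.** b2 = −0.511, average = (0.673 − 0.511)/3 = 0.054.
- Adenocarcinoma: 0.7 × 0.336 + 0.3 × 0.054 = 0.252, HR 1.29.
- Squamous: 0.7 × (−0.511) + 0.3 × 0.054 = −0.341, HR 0.71.

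**Simulation of the strong case.** The set-up was 400,000 people, BMI missing at random, baseline 10-year risks of 2% and 1%, and proper normal imputation. Imputing on the overall indicator and its Nelson-Aalen term gave:

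| Missing | Adenocarcinoma HR (true 1.40) | Squamous HR (true 0.60) |
|---|---|---|
| 20% | 1.32 | 0.68 |
| 30% | 1.28 | 0.71 |
| 40% | 1.24 | 0.75 |

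Using both subtype indicators and their Nelson-Aalen terms instead, at 30% missing, recovered 1.40 and 0.60.

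**Second simulation, different inputs.** This used 400,000 people and 15 replicates, with BMI missing completely at random. The true log HRs per SD were +0.30 (adenocarcinoma), −0.30 (squamous) and +0.25 (incident Barrett's). Age was in both the imputation and analysis models.

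| Missing | Imputation outcome terms | Adenocarcinoma | Squamous | Barrett's | All types |
|---|---|---|---|---|---|
| 20% | none needed (full data) | 0.304 | −0.296 | 0.251 | 0.118 |
| 20% | overall cancer only | 0.264 | −0.211 | 0.197 | 0.117 |
| 20% | subtypes and Barrett's | 0.304 | −0.294 | 0.250 | 0.118 |
| 40% | none needed (full data) | 0.302 | −0.304 | 0.241 | 0.113 |
| 40% | overall cancer only | 0.228 | −0.137 | 0.143 | 0.114 |
| 40% | subtypes and Barrett's | 0.306 | −0.310 | 0.236 | 0.114 |

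Monte Carlo standard errors were 0.003 to 0.015. With the overall indicator only, the adenocarcinoma–squamous gap falls from 0.60 to 0.48 at 20% missing (0.264 + 0.211) and from 0.61 to 0.37 at 40% (0.228 + 0.137). This agrees with the (1 − p) rule. The all-types coefficient does not move.

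**Townsend.** Section 6.8.3 lists five variables with missing values: ethnicity, Townsend, BMI, smoking and alcohol. Section 6.8.6 lists four: ethnicity, BMI, alcohol and smoking. The difference is Townsend.

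**The case against.** **The wording may mean more than it says.** Section 6.8.3 uses plurals for both the indicators and the Nelson-Aalen estimators, and section 6.4 treats oesophageal cancer as including its subtypes. The parenthesis could thus be shorthand for overall and subtype indicators together. A full list of imputation terms is also often left to an SAP. This has some force, and the authors may have intended the wider set. But the protocol does specify the outcome terms, and it introduces them with a word that restricts. An analyst who follows the text would enter the overall indicator alone, so the wording needs correcting on either reading.

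**The bias may be small.** This stands as a limit on size. A reader shown only the 1.40 and 0.60 case might infer that the subtype equations are badly biased whatever the data. The documents do not support that: with 1.40 and 1.20 the shift is slight, and with equal subtype effects it vanishes. No effect on 10-year risk, calibration or discrimination has been shown.

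**Other stronger readings that do not hold.**
- A reader might infer that the all-types equation is compromised. It is essentially unbiased.
- A reader might take a Barrett's model as firmly planned. Section 6.8.1 points that way, but section 6.8.2 runs the risk period for all analyses to oesophageal cancer diagnosis, so the Barrett's part is conditional.
- A reader might infer that all adenocarcinoma and squamous cases with missing data draw from one distribution. They do so only given the same predictors and follow-up. Richer predictors would not remove the bias.
- A reader might infer that validation patients without a Townsend score will be excluded. Section 6.8.6 does not say so. Their handling is unstated, and the omission may be a slip.

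**Conclusion.** The concern holds in a limited form. Followed as written, section 6.8.3 imputes without the subtype outcomes, and the subtype models are fitted on the result. Where covariate effects differ by histology, the gap between subtype log hazard ratios shrinks by roughly the missing fraction. At 30% missing this ranges from slight (1.40/1.20 to about 1.38/1.24) to substantial (1.40/0.60 to about 1.28/0.71). A Barrett's model, if fitted, is attenuated: 0.251 to 0.197 at 20% missing and 0.241 to 0.143 at 40%.

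These figures rest on assumed effects, assumed missing fractions, a 2:1 ratio of baseline rates and values missing at random. The direction does not depend on the particular values. The five-versus-four mismatch on Townsend is a plain inconsistency. Its effect cannot be sized, because the missing fraction is not given, and it matters only if Townsend stays in the final equation.

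**What to change.** In section 6.8.3, replace the parenthesis that restricts the outcome indicators to oesophageal cancer. Name separate event indicators for adenocarcinoma and squamous cell cancer, each with its own Nelson-Aalen cumulative hazard, and add incident Barrett's with its own term if that outcome is modelled. Running one imputation per outcome is an acceptable alternative. Further terms, such as death or other and unknown histology, are not needed to repair this defect.

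In section 6.8.6, add Townsend score to the variables imputed in the validation data, so that the list matches section 6.8.3.

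The cost is a few more terms in the chained equations and a slightly longer run time. The change should be made before derivation, since correcting it later would mean re-imputing and refitting.
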